## 8.5.9. Change from Baseline in QoL-B Domain Scores to Weeks 16, 28, 40, and 52 in Adult Participants

The change from baseline in QoL-B Domain scores at Weeks 16, 28, 40, and 52 in which all observed data of adult participants will be included in the analysis and will use The ITT Analysis Set (see Section 5.2).

QoL-B Domain Scores and changes from baseline will be summarized and statistically analyzed by domain like the analysis of QoL-B Respiratory Symptoms Domain Score in Section 8.3.5.1. A separate figure for each domain will be provided. As adult participants will have data only, the age group will be removed from the statistical model.

## 8.5.10. PGI-C and the Change from Baseline in PGI-S at Weeks 16, 28, 40, and 52 in Adult Participants

The PGI-C and the PGI-S change from baseline in at Weeks 16, 28, 40, 52 in which all observed data will be included in the analysis will be presented and will use the ITT Analysis Set (see Section 5.2).

PGI-S and PGI-C will be summarized by treatment group. PGI-S will be tabulated using a shift from baseline at visits 16, 28, 40, and 52, while PGI-C will be summarized by visit. As adult participants will have data only, the age group will be removed from the statistical model. Completion rates will be presented by time point (see Section 6.7.5.10).

### 8.5.11. Rate of Change in Prebronchodilator and Postbronchodilator FEV1 Over the 52-Week Treatment Period

The rate of change in prebronchodilator and postbronchodilator FEV1 over the 52-Week treatment period in which all observed data will be included in the analysis will be presented and will use the ITT Analysis Set (see Section 5.2) The derivation of the endpoint is detailed in Section 6.7.3.

The rate of change will be summarized descriptively by prebronchodilator and postbronchodilator and displayed by brensocatib dose levels and placebo.

CONFIDENTIAL Page 71 of 139

Prebronchodilator and postbronchodilator FEV1 will each be analyzed using a linear random coefficients model including treatment group as a categorical fixed effect, time (in weeks) as continuous fixed effect, the treatment-by-time interaction, a random time coefficient for subject, and a random intercept for subject. The variance-covariance structure for the random effects will be unstructured. This analysis will be performed in SAS using the MIXED procedure. The OM option will be used to adjust the coefficients for the LSMEANS to reflect the observed data.

The equations for the fitted line for each treatment group will be presented.

Change from baseline values will be displayed along with the regression line in a graph. The actual study day will be used at the time axis.

### 8.5.12. Change from Baseline in BEST-CT and AA Scores at Week 52

Analysis of CT substudy endpoints will be described in a separate SAP.

### 8.5.13. Change from Baseline in Concentration of Biomarkers (NE, CatG, PR3) in Sputum to Week 52

Please refer to Section 11.1.

### 8.5.14. Change from Baseline in Concentration of Biomarkers (NE, CatG, and PR3) in Blood to Week 52

Please refer to Section 11.2.

CONFIDENTIAL Page 72 of 139

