assessed by the EuroQoL-5D-5L over the 52-week treatment period	
9. To evaluate the effect of brensocatib compared with placebo on QOL, as assessed by the QOL-B domains over the 52-week treatment period in adult subjects	Change from Baseline in QOL-B domain scores to Weeks 16, 28, 40, and 52 in adult subjects
10. To evaluate the effect of brensocatib compared with placebo on PGI-S and PGI-C scales over the 52-week treatment period in adult subjects	Change in PGI-S and PGI-C from Baseline to Weeks 16, 28, 40, and 52 in adult subjects
11. To evaluate the effect of brensocatib compared with placebo on the rate of decline in prebronchodilator and postbronchodilator FEV 1 over the 52-week treatment period	Rate of change in prebronchodilator and postbronchodilator FEV 1 over the 52-week treatment period
12. To evaluate the effect of brensocatib compared with placebo on the progression of lung damage as evaluated by CT scan over the 52-week treatment period	Change from Baseline in BEST-CT and Airway-Artery scores at Week 52
13. To evaluate the effect of brensocatib compared with placebo on the concentration of biomarkers (NE, CatG, PR3) in sputum over the 52-week treatment period	Change in concentration of sputum NE, CatG, and PR3 from Baseline to Week 52
14. To evaluate the effect of brensocatib compared with placebo on the concentration of biomarkers (NE, CatG, PR3) and neutrophil functions in blood over the 52-week treatment period	Change in concentration of blood NE, CatG, PR3, and neutrophil functions from Baseline to Week 52
15. Population PK analysis	Estimated PK parameters (eg, C max , AUC, t ½ ) using population PK analysis approach. Specified in a separate SAP
16. Population PK/PD relationship evaluation	Relationships between brensocatib exposure and response (safety, efficacy, and biomarker measurements) over the 52-week treatment period. Specified in a separate SAP

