PGI-S q		X					Compl	ete every 2 v	veeks			
PGI-C q							Compl	ete every 2 v	veeks			
EQ-5D-5L/ QOL-PCD – Completion at site r		X	X		X		X		X		X	X
Blood PK samples 		X	X		X		X		X		X	
Sputum PD sample t	X	X	X		X		X		X		X	X
For substudy only: blood PD u	X	X	X		X		X		X		X	X
Health resource utilization V			X	X	X	X	X	X	X	X	X	

Study Period	Screen		Treatment Period									Follow-Up
Study Days Study Weeks	Days -42 to -1	D1 (Baseline)	D28 Wk4	D70 Wk10	D112 Wk16	D154 Wk22	D196 Wk28	D238 Wk34	D280 Wk40	D322 Wk46	D364 Wk52 (EOT or E/D) a	D392 Wk56 (EOS)
Visit	V1	V2	V3	Phone V4 b	V5	Phone V6 b	V7	Phone V8 b	V9	Phone V10 b	V11	V12
Collect days of work/ school missed			X	X	X	X	X	X	X	X	X	
Dispense study drug, accountability of returned drug, and review of dosing diary W		X	X		X		X		X		X w	X w
Adverse events collection		X	X	X	X	X	X	X	X	X	X	X
Assessment of skin conditions (hyperkeratosis of palm and soles) x		X	X		X		X		X		X	X
Assessment of periodontitis y		X	X	X	X	X	X	X	X	X	X	X

Note: for each of the Study Visits from Visit 3 to End of Study (Visit 12), there is a ±7-day window.

<sup>a Visit 11 (Week 52) is completed for those who finish study treatment per protocol. The visit is alternatively completed for those who discontinue early from study treatment.

b For Phone Visits, collect data outlined in Phone Visit Sheet: exacerbations, safety events, hospitalizations, or emergency room visits (including start and end date, follow-up with facility to retrieve source documentation), days of work missed (including start and end date), IV antibacterial drug use (including start and end dates), list of new rescue medications (including name, and start and end dates).

<sup>c Demographics and medical history: At Visit 2 (Baseline) only medical history collected.

<sup>d Height, weight, and BMI: Body weight will be measured at Screening and at the Week 52 (Visit 11; EOT). For adult subjects, the measurement of height, without shoes, will be performed at Screening Visit only. For adolescent subjects, measurement of height, without shoes, will be performed at Screening Visit and Visit 11 (EOT).

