#### 8.3.3.1. Main Analyses

The Main Estimand of the change from baseline in post-bronchodilator FEV1 (L) at Week 52 is the On-Study Estimand in which all observed data will be included in the analysis (see Section 2). The ITT Analysis Set (see Section 5.2) will be used for this Estimand. The derivation of the endpoint is detailed in Section 6.7.3. Tabulations described below will not be limited to Week 52 but summarize all scheduled time points.

Pre- and post-bronchodilator FEV1 assessments at baseline and Weeks 16, 28, 40, 52 will be summarized by treatment group using descriptive statistics. The summary will include changes from baseline, too.

Change from baseline in post-bronchodilator FEV1 (L) will be analyzed using a linear repeated measures model including treatment group, visit, treatment-by-visit interaction, sputum sample being classified as positive or negative for *Pseudomonas aeruginosa* at Screening Visit, the number of prior PEs [<3 or  $\ge$ 3] in the previous 12 months, stratification region (North America, Europe, Japan, and the Rest of the World), and age group (adult, adolescent) as fixed effects, and baseline value as covariate. The variance-covariance structure will be compound symmetric with the robust sandwich variance estimator (option EMPIRICAL in the PROC-Statement). This analysis will be performed in SAS using MIXED procedure. The OM option will be used to adjust the coefficients for the LSMEANS to reflect the observed data.

If the age group covariate creates estimability issues, it may be removed. If the model still does not converge after removing the age group covariate, other handling including using the parametric covariance estimator instead of the robust sandwich covariance estimator may be applied. When using the parametric covariance estimator, the restricted maximum likelihood (REML) estimator will be applied, with the variance-covariance structure being applied with the following sequence: UN -> TOEPH -> ARH(1) -> CSH. If the model still does not converge, the maximum likelihood estimator will be applied instead of the REML estimator, with the same sequence of the possible variance-covariance structures. The adjustment will be added to the footnote of the corresponding outputs.

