#### 8.3.6. Subgroup Analyses

Subgroup analyses for all secondary endpoints will be reported for the On-Study Estimand based on the groupings defined in Section 8.2.6. However, analyses of QoL-B which is applicable for adults only, will exclude the adolescent subgroup. In addition, the main analysis for secondary endpoints will be repeated for the adolescent subgroup (12-<18 years of age), and separately for the adult subgroup for the On-Study estimand.

Subgroup analysis will be displayed in tabulations and forest plots.

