# Random coefficients regression model for Rate of Change in Prebronchodilator and Postbronchodilator $FEV_1$ Over the 52-Week Treatment Period

```
PROC MIXED DATA=... METHOD=REML;
CLASS trtp subject;
MODEL FEV1=trtp time trtp*time / S OUTP=prediction DDFM=KR;
RANDOM intercept time / TYPE=UN SUB=SUBJECT;
ESTIMATE "Regr. coeff. Brensocatib 10mg QD" time 1 time*trtp 1 0 0/CL;
ESTIMATE "Regr. coeff. Brensocatib 25mg QD" time 1 time*trtp 0 1 0/CL;
ESTIMATE "Regr. coeff. Placebo QD" time 1 time*trtp 0 0 1/CL;
RUN;
```

CONFIDENTIAL Page 133 of 139

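### The planned FEV1 slope analysis names no dose-minus-placebo difference with a confidence interval, and it pools adults and adolescents, allocated in different ratios, without an age group-by-time term

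*SAP*

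**What the plan says.** Protocol 2.3, Table 3, objective 11 is comparative: "To evaluate the effect of brensocatib compared with placebo on the rate of decline in prebronchodilator and postbronchodilator" FEV1 over the 52-week treatment period.

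SAP 8.5.11 analyses pre- and postbronchodilator FEV1 on the ITT set with a "linear random coefficients model including treatment group as a categorical fixed effect, time (in weeks) as continuous fixed effect, the treatment-by-time interaction", plus a random intercept and random time coefficient per subject. The outputs it names are a descriptive summary by arm, a graph, and this: "The equations for the fitted line for each treatment group will be presented". SAP Table 8 gives the population-level summary for this endpoint as a slope, whereas many other exploratory rows give a mean difference. SAP 6.7.3, cited for the derivation, defines change and percentage change but no slope.

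The Appendix I code is "MODEL FEV1=trtp time trtp*time / S OUTP=prediction DDFM=KR". Three ESTIMATE statements with CL follow, one slope each for 10 mg, 25 mg and placebo. None is a difference between arms.

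Neither the text nor the code has an age term. The Week 52 FEV1 model in SAP 8.3.3.1 does include age group. Adults are randomised 1:1:1 (540 per arm) and adolescents 2:2:1 (16:16:8).

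**The concern.** There are two gaps in one analysis.

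**Missing contrast.** The objective concerns a difference between arms, but the plan names only the arm-specific slopes. Three slopes with separate intervals do not give the interval for a difference. SAP section 1 treats any analysis not described in the plan and run after unblinding as post hoc, so an interval for the difference added later could carry that label. SAP section 13 lists changes to several Protocol 2.3 endpoints but not to this one, so the gap reads as an omission and not as a decision.

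**Pooling.** FEV1 in litres can be expected to rise with growth at ages 12 to 17. The protocol re-measures height at the end of treatment in this group only: "For adolescent subjects, measurement of height, without shoes, will be performed at Screening Visit and Visit 11 (EOT"). Adolescents are about twice as large a share of each brensocatib arm as of placebo. Without an age group-by-time term, any difference between adolescent and adult slopes passes into the treatment slopes in proportion to that imbalance. No adult-only repeat is planned for this endpoint, so no planned output would show it.

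**Working it through.** **The plan's own figures.** The documents give no sample size, power or SD for the slope. The allocation figures reproduce: 1620/3 = 540 adults per arm; 40 × 2/5, 2/5, 1/5 = 16, 16, 8 adolescents.

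**What the code yields.** The placebo ESTIMATE uses coefficients `0 0 1`, so placebo is the last class level and therefore the default reference. Option `S` prints the fixed-effect solution. Its treatment-by-time rows are then each dose's slope minus the placebo slope, with SE and p-value. The MODEL statement has no `CL` option, so that table carries no interval, and nothing in the text identifies those rows as the result.

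**Imbalance.**
- Each brensocatib arm: 16/(540 + 16) = 16/556 = 2.88%.
- Placebo: 8/(540 + 8) = 8/548 = 1.46%.
- Difference: 0.01418.

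**Shift in a slope difference** = 0.01418 × (adolescent slope minus adult slope). The gap is an assumption:

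| Assumed gap (L/year) | Shift toward brensocatib (mL/year) |
|---|---|
| 0.10 | 1.4 |
| 0.20 | 2.8 |
| 0.30 | 4.3 |

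**Against sampling error.** SE of a slope difference = SD × √(1/556 + 1/548) = SD × 0.0602. For an assumed SD of individual annual slopes of 150 to 300 mL/year, the SE is 9.0 to 18.1 mL/year. The shift is then between 1.42/18.1 = 0.08 SE and 4.25/9.0 = 0.47 SE.

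**Which term removes it.** The expected slope difference was computed by generalised least squares for the SAP's random-coefficients model. Visits were at Weeks 0, 16, 28, 40 and 52, the true treatment effect was zero, and the assumed gap was 0.30 L/year. Assumed SDs were 600 mL (intercept), 150 mL/year (slope) and 120 mL (residual).

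| Model | Expected dose-minus-placebo slope (mL/year) | SE (mL/year) |
|---|---|---|
| As in the SAP | +4.25 | 12.93 |
| Plus age group main effect | +4.25 | 12.93 |
| Plus age group and age group-by-time | 0.00 | 12.94 |

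A main effect moves the level of the line, not its slope, so it leaves the shift unchanged. The interaction removes it at almost no cost in precision.

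**The case against.** **The comparison is already in the model.** Treatment-by-time is fitted, option `S` prints both differences with SE and p-value, and SAP 8.1 says that the comparisons shown are those against placebo. This stands as far as it goes. A reader might infer that objective 11 cannot be answered, and the documents do not support that. What remains is narrower: no interval is requested for the difference, and no text or code names it as the result.

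**The endpoint is exploratory.** It lies outside the 12 hypotheses of the gatekeeping procedure, so no confirmatory conclusion depends on it. This stands and sets the severity.

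**The direction of the shift is assumed.** A reader might infer that the slopes are known to favour brensocatib. The documents give no FEV1 growth figure; repeat height measurement in adolescents fits with growth but does not quantify it. The primary lock is triggered by adults, so some adolescents may have partial follow-up and a different weight from full 16:16:8. The shift is conditional and small.

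**Does the Week 52 FEV1 analysis share the flaw?** A reader might think so, since its age term has no interaction with visit and is subject to the clause "If the age group covariate creates estimability issues, it may be removed". With the age main effect kept, the residual at Week 52 is about (1 − 34/52) × 1.4 to 4.3 = 0.5 to 1.5 mL, where 34 is the mean of Weeks 16, 28, 40 and 52. SAP 8.3.6 and Protocol 10.4.6.5 already plan an adult-only repeat. No change is needed there.

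**Is the adolescent subgroup in litres misleading?** SAP 8.3.6 states that "the main analysis for secondary endpoints will be repeated for the adolescent subgroup (12-<18 years of age"). Between randomised arms, variation in growth is noise and not bias, and the plan claims only directional trends from about 40 adolescents. Asking for percent predicted FEV1 there would be a preference and not the correction of an error.

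**Conclusion.** The point holds as a minor gap in specification and reporting. Followed as written, SAP 8.5.11 and Appendix I deliver three slopes and fitted lines but not the dose-minus-placebo difference with an interval that objective 11 calls for. That part rests on the documents alone.

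The pooling point holds in structure: unequal adolescent shares, no age group-by-time term, and no adult-only repeat for this endpoint. Its size rests on two assumptions from outside the documents, the growth gap and the SD of individual slopes, and on full 16:16:8 follow-up. Under the ranges used, the shift stays below half a standard error. It would not by itself create an apparent benefit, but it is avoidable and is best corrected in the same edit.

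**What to change.** In SAP 8.5.11 and the Appendix I code, before unblinding:

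1. Add two statements and name their output as the objective 11 result, for pre- and postbronchodilator FEV1 separately:
   - `ESTIMATE 'Slope difference, 10 mg minus placebo' time*trtp 1 0 -1 / CL;`
   - `ESTIMATE 'Slope difference, 25 mg minus placebo' time*trtp 0 1 -1 / CL;`
2. Add age group and age group-by-time as fixed effects, or fit the slope model in adults only. An age group main effect alone is not enough.
3. Change the Table 8 summary for this endpoint from a slope to a difference in slopes.

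The cost is a few lines of code and text and one or two degrees of freedom. No new data are needed, since age and spirometry are already collected. The Week 52 FEV1 model and the adolescent subgroup analysis can stay as they are.

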### 9. SAFETY

Unless otherwise stated all summaries will have corresponding listings.

Data collected in the safety monitoring (i.e., follow-up after discontinuation of randomized IP) will be analyzed separately, see Section 9.14 for details.

The Safety Analysis Set (see Section 5.3) will be utilized, if not specified otherwise.

### 9.1. Exposure to IP, Compliance, and IP Interruption

Exposure to IP will be descriptively summarized by treatment group including the below (see Section 6.4.7 for derivation of data points):

- Duration of treatment of IP,
- Duration of treatment with IP by categories:
  - o <4 weeks
  - o <12 weeks
  - $\circ$  >=12 weeks to <24 weeks
  - $\circ$  >=24 weeks to <36 weeks
  - $\circ$  >=36 weeks to <=52 weeks
  - $\circ$  >52 weeks,
- Cumulative duration of treatment with IP by categories:
  - $\circ$  >=12 weeks,
  - $\circ$  >=24 weeks,
  - $\circ$  >=36 weeks.
- Duration of IP exposure,
- Duration of IP exposure by categories:
  - o <4 weeks
  - o <12 weeks
  - $\circ$  >=12 weeks to <24 weeks
  - $\circ$  >=24 weeks to <36 weeks
  - $\circ$  >=36 weeks to <=52 weeks
  - $\circ$  >52 weeks,
- Cumulative duration of IP exposure by categories:
  - $\circ$  >=12 weeks,
  - $\circ$  >=24 weeks,
  - $\circ$  >=36 weeks.
- Number and percent of participants compliance to IP, categorized as:
  - >120%, >100-<=120%, >=75-<=100%, <75%,
- Number and percent of participants missed (at least one) IP intake,
- Basic summaries of number of days a participant missed IP intake,
- Number and percent of participants who missed IP due to COVID-19.

CONFIDENTIAL Page 73 of 139

<sup>6 The category "<4 weeks" will be a single category for duration of treatment of IP as well as for the duration of IP exposure.

A cross tabulation of IP randomized and IP received (actual received) will be generated by treatment group and dispensed visit, e.g., Day1, Week 4, Week 16, Week 28, and Week 40. The tabulation will count the number of participants as well the number of incorrect doses. The IP received category will separately count randomized but not treated participants.

In addition, the below listings will be produced:

- IP used from specific batches as provided by the interactive response system,
- randomization scheme and codes.

### 9.2. Adverse Events

The AE verbatim descriptions (Investigator terms from the eCRF) will be classified into standardized medical terminology using MedDRA. Adverse events will be coded to primary SOC and PT using the most recent MedDRA version.

Treatment-emergent adverse event (TEAEs) are those AEs that occurred on or after the date of first dose of IP and within 28 days after the last dose of IP. AEs that occur between the time participant signs the ICF for the study and the time when participant receives his/her first dose of IP on Study Day 1 will be summarized as medical history and not as a TEAE unless the event meets the definition of a serious AE (SAE).

Where AE start dates are missing or partially missing, AEs will be assumed to be treatmentemergent, except if the partial start dates or the AE end date indicate that the AE started before the first administration of IP (see Table 9).

Table 9: TEAE	Assignment in	Case of Missing	AE Start Date	Elements
Table J. ILAL	A331211111C111 111	Case of Milssills	Z AL Start Date	Licinchis

Missing elements of AE start	Rule (study drug start = first dose of IP)	Classification
	ssing information for AE start:	
Regardless of any finis	non-TEAE	
Otherwise (i.e., if AE end date ≥ IP start date)		
- day/month/year	all AEs	TEAE
day and month	AE start year ≥ IP start year	TEAE
- day and month	AE start year < IP start year	non-TEAE
1	AE start month/year ≥ IP start month/year	TEAE
- day	AE start month/year < IP start month/year	non-TEAE

Duration of AEs will be calculated in days (see Section 6.4.5). If date of onset or end date of event is missing, duration will be set to missing.

CONFIDENTIAL Page 74 of 139

<sup>7 An AE that begin in screening but worsen during the treatment period will be reported as TEAE as the investigators are asked to enter a new event into the eCRF.

<sup>8 Date of last IP administration will be collected from EOT form where the leading question "Last dose date" is recorded.

Tabulations that are displayed by SOC and PT will be ordered by descending order of total incidence of SOC, and PT within each SOC. Tabulations of the following types will be presented:

- Overall incidence of TEAEs including the incidence of participants with at least one:
  - o TEAE,
  - o serious TEAE,
  - o severe TEAE,
  - TEAE resulting in death,
  - TEAE related to IP,
  - o serious TEAE related to IP,
  - o TEAE of Special Interest (TEAESI),
  - TEAE leading to withdrawal from IP
  - o TEAE leading to withdrawal from study, and
  - o COVID-19 TEAE; will be identified through PTs as indicated in Appendix K
- Incidence of COVID-19 TEAEs including the incidence of participants with at least one of the below will be presented overall and by months. By months derivation will follow the algorithm used in Section 6.7.1.7. The AE start date will be considered. COVID-19 TEAEs will be identified through PTs as indicated in Appendix K:
  - o TEAE,
  - o serious TEAE,
  - o severe TEAE,
  - TEAE resulting in death,
  - TEAE related to IP,
  - o serious TEAE related to IP,
  - o TEAE leading to withdrawal from IP, and
  - o TEAE leading to withdrawal from study.
- Participant's incidence of TEAEs by MedDRA SOC and PT:
  - o TEAEs,
  - o severe TEAEs,
  - o serious TEAEs,
  - o TEAEs related to IP,
  - o serious TEAEs related to IP,

CONFIDENTIAL Page 75 of 139

- o TEAEs resulting in Death,
- o TEAEs leading to IP withdrawal,
- o TEAEs leading to study withdrawal,
- o COVID-19 TEAEs will be identified through PTs as indicated in Appendix K.
- Participant's incidence of TEAEs by relationship to IP by MedDRA SOC and PT.
- Participant's incidence of TEAEs by MedDRA SOC, PT, and maximum severity. (A participant will be classified at the highest reported severity at PT level. Missing severity will be classified as missing on the summary if there is no non-missing severity at the level of summarization.).
- Participant's incidence of TEAEs by MedDRA PT.
- Correlation between COVID-19 AEs within + 30 days of an exacerbation event that meet the protocol definition of PE diagnosis based on independent adjudication process start and end date; COVID-19 AEs will be identified through PTs as indicated in Appendix K.

For those participants who had at least one serious TEAE, TEAESI, or TEAE leading to withdrawal of IP, all information pertaining to AEs noted during the study will be presented in a participant listing. Non-treatment-emergent AEs will be listed separately.

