# 9.11. Reporting Requirements

#### 9.11.1. Adverse Events

All AEs will be reported on the Adverse Events Form of the eCRF. Adverse events that occur between the time subject signs the ICF for the study and the time when subject receives his/her first dose of study treatment on Day 1 will be summarized as medical history and not as a TEAE unless the event meets the definition of an SAE as defined below.

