### 9.14. Summary of Data After Early Discontinuation of IP

All participants are encouraged to stay in the study regardless of IP discontinuation. Any participants who discontinue from IP will have their reason for discontinuing IP recorded and will continue in the study with their remaining scheduled study visits. The eCRF collection of data does not distinguish visits relative to IP termination milestone, therefore for the purpose of the analysis observations will be flagged if collected after IP early discontinuation. An additional timing variable will be introduced to reflect Study Day relative to EOT for visits occurring beyond treatment discontinuation.

Descriptive summaries will be presented for the subgroup of participants who discontinues IP early based on the available data through the EOS visit. For safety parameters these summaries will present data after 28 days following the last IP intake (>EOT+28 days). The summaries will be limited to the following assessments:

- AE, SAEs and AESIs,
- Laboratory and vital signs assessments.
- Deaths will be listed.

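### SAP Table 9 sets no upper limit on adverse events with partial start dates, and the clause on SAEs before first dose in SAP 9.2 needs rewording

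*SAP*

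**What the plan says.** SAP 9.2 gives a window with two ends. "Treatment-emergent adverse event (TEAEs) are those AEs that occurred on or after" "the date of first dose of IP and within 28 days after the last dose of IP".

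For missing or partial start dates, the same section assumes the event is treatment-emergent. The only exception is where the partial start or the end date shows that it began before first dose. Table 9 puts this into rules. Once an end date before first dose has been ruled out, a record lacking only the day is a TEAE if "AE start month/year ≥ IP start month/year". A record lacking day and month is a TEAE if its year is the year of first dose or later. A record with no start date at all is always a TEAE. No row mentions last dose. SAP 6.9.3 states that adverse event dates will not be imputed, so no imputed date can bring the limit back.

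Elsewhere the SAP treats late events as off treatment. SAP 6.6 puts safety data collected beyond the 4-week follow-up after early discontinuation outside the treatment-emergent period and labels the adverse events accordingly. SAP 9.14 says: "For safety parameters these summaries will present data after 28 days following the last IP intake".

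On events between consent and first dose, SAP 9.2 says that they "will be summarized as medical history and not as a TEAE unless the event meets the definition of a serious AE (SAE". Protocol 9.11.1 has nearly the same clause: "and not as a TEAE unless the event meets the definition of an SAE as defined below".

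**The concern.** Whether an event is a TEAE should depend on when it began relative to treatment. Under Table 9, two events that began on the same day after the window closed can be classified in opposite ways, depending only on whether the site recorded the day. The fully dated one is not a TEAE and belongs in the SAP 9.14 summary. The one lacking the day enters the TEAE tables. The SAP does not say which section prevails, so programmers could resolve it differently.

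TEAE status feeds every incidence table in SAP 9.2. It also feeds the AESI risk differences with exact 95% confidence intervals in SAP 9.3. Events long after drug was stopped would be attributed to the assigned treatment, and unevenly if early stopping differs between arms.

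The clause on SAEs before dosing raises a second question about the same window: does a serious event during screening, before randomization and before any drug, count as treatment-emergent?

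**Working it through.** The plan gives no figure to reproduce, so the check is to apply its rules to dates.

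**One event under the two rules.** Assume first dose on 10 Jan 2023 and last dose on 10 Feb 2023.
- The window closes on 10 Feb 2023 + 28 days = 10 Mar 2023.
- The onset is recorded as Aug 2023 with the day missing, so the earliest possible onset is 1 Aug 2023.
- 10 Mar to 1 Aug 2023 = 144 days, so the event lies outside the window whatever the missing day is.
- Table 9: Aug 2023 is not before Jan 2023, so the event is a TEAE.
- The same event dated 15 Aug 2023 is not a TEAE and falls under SAP 9.14.

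**Who can be affected.** Assume first dose on 10 Jan 2022 and an end-of-study visit on Day 392 (Week 56 in the schedule). For last dose on Day d, follow-up beyond the window is 392 − (d + 28) days. The last two columns count the calendar months up to the end of study that lie wholly after the window and are classed as TEAE.

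| Last dose (day) | Window closes | Days followed after the window | Months classed TEAE, Table 9 as written | With an upper limit |
|---|---|---|---|---|
| 28 | 6 Mar 2022 | 392 − 56 = 336 | 11 | 0 |
| 112 | 29 May 2022 | 392 − 140 = 252 | 9 | 0 |
| 196 | 21 Aug 2022 | 392 − 224 = 168 | 6 | 0 |
| 280 | 13 Nov 2022 | 392 − 308 = 84 | 3 | 0 |
| 364 | 5 Feb 2023 | 392 − 392 = 0 | 0 | 0 |

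Year-only dates behave the same way. With last dose on 6 Feb 2022 (Day 28), an onset recorded only as 2023 is a TEAE under Table 9, although the window closed on 6 Mar 2022.

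For someone who completes treatment, the scheduled end of study falls on the last day of the window. Only the ±7-day visit allowance could leave a few days beyond it.

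**SAE before dosing.** Take an SAE starting 21 days before first dose.
- Main definition in SAP 9.2: not a TEAE, because onset precedes first dose.
- The exception for SAEs, read literally: TEAE.
- Partial-date rule, if the known month precedes the month of first dose: not a TEAE, because Table 9 makes no exception for seriousness.

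SAP 9.2 thus gives two answers for a fully dated event, and the partial-date rule sides with the main definition.

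**The case against.** Assuming treatment emergence when a date is incomplete is a standard conservative rule. That is right for a wholly missing date, or for a month that straddles the end of the window, and nothing here argues against it. It does not cover a known month or year that lies entirely after the window, because such a date leaves no doubt to resolve. It is also true that SAP 6.6 and 9.14 already show the intended handling. That makes the correction easy, but Table 9 is the rule for incomplete dates and it says otherwise.

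A reader might infer that the SAP certainly counts SAEs before dosing as TEAEs. The documents do not establish this. The exception can be read as attached to the medical-history part of the sentence, so that a serious event stays in adverse event reporting and is not moved to medical history. The setting supports that reading: Protocol 9.11.1 sits among the reporting requirements, directly before the SAE reporting rules. SAP 6.4.5 also takes first dose as the reference date for treatment emergence. SAP 9.2 already provides for a separate listing of non-treatment-emergent events, so a place for these SAEs exists. What remains is that the literal wording contradicts the preceding sentence and neither document says which meaning applies. Worsening of a screening event does not explain the clause, because a footnote in SAP 9.2 already treats that as a new event.

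**Conclusion.** The missing upper limit is a definite inconsistency between Table 9 and the SAP's own TEAE definition, 6.6 and 9.14. Its reach is narrow. The participant must stop drug early, stay in the study (which is encouraged, not assured), and have an event whose incomplete start date lies wholly after last dose + 28 days. The documents give no event counts and no rate of partial dates, so the number affected cannot be computed. It is probably small. The clause on SAEs before dosing is an ambiguity to settle, not a demonstrated error.

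A reader might go further and infer that such SAEs would hide a real difference between arms. The documents do not support that. If a proportion p in each arm has an SAE before dosing, independent of arm and of later events, the risk of at least one event goes from r to p + (1 − p)r, and the risk difference is multiplied by (1 − p). A deliberately high value of p takes all 1,660 planned participants through the full 42 days: 1,660 × 42/365.25 = 190.9 person-years. At an assumed 10 to 20 SAEs per 100 person-years this gives 19 to 38 events, so p is at most 19/1,660 = 1.1% to 38/1,660 = 2.3%. A risk difference of 3.0 points would become about 2.97 to 2.93, a slight attenuation.

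Nor should the ratio of screening to treatment time, about 42/365, be taken as the share of serious TEAEs affected. Many seriously ill people fail screening. The Safety Analysis Set admits only those later dosed, so a death before dosing cannot enter the tables. The Schedule of Assessments also marks adverse event collection only from Visit 2, although Protocol 9.11.1 covers events from consent. No efficacy conclusion is affected.

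**What to change.** In SAP Table 9, add a row: if the earliest onset compatible with the known parts of the start date falls after last dose + 28 days, the event is non-TEAE and is reported under SAP 9.14. Keep the TEAE assignment for fully missing start dates and for partial dates that straddle the end of the window. Add the matching exception to the sentence above the table.

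In SAP 9.2, replace the exception for SAEs with a statement that SAEs with onset before first dose are kept as adverse events, listed as non-treatment-emergent and not counted as TEAEs. Note in SAP 13 that this clarifies Protocol 9.11.1; the protocol text itself can be aligned if it is next amended.

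The cost is one table row, two sentences and a note, plus a small change to the program that sets the TEAE flag. No data collection changes. It should be settled before unblinding, so that the classification is fixed without knowledge of treatment.
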